# PROTOCOL SUMMARY

1.1 SYNOPSIS			
STUDY TITLE	A Feasibilty Study to Evaluate the Clinical Safety of ENvizion™ Nasoenteral Feeding Tube Placement using the ENvizion™ ENVUE System in Patients.		
PROTOCOL NUMBER	NUTRI-002		
DEVICE DESCRIPTION	The ENvizion™ ENVUE™ System is designed to aid qualified operators in the placement of the ENvizion™ NasoEnteral Tube™ of 10 Fr to 12 Fr into the stomach or small intestine of patients requiring enteral feeding. The ENVUE System is intended as an adjunct to current placement practices for assisting clinical practitioners who place feeding tubes in adult patients.		
	The ENvizion™ NasoEnteral Tube has been specifically designed for use with the ENVUE™ System and is intended for placement in the stomach or small intestine. It is intended for use in adult patients who require intermittent or continuous feedings via the nasogastric or nasoenteric route.		
STUDY OBJECTIVES	The objective of this study is to assess the safety of the ENVUE System as an adjunct to current practices for placement of nasoenteral feeding tubes.		
STUDY DESIGN	The study is a prospective, single center, non-randomized clinical trial in patients that require placement of a nasoenteral feeding tube as a result of their current medical condition.		
NUMBER OF SUBJECTS AND SITES	Up to fifty (50) subjects and at least forty (40) will complete the Procedure Visit (NasoEnteral Tube placement procedure, section 1.3) at a single center by at least five operators. This number (40-50 subjects) does not include screen failures. Envizion nasoenteral feeding tubes will be placed in 5 run-in subjects prior to enrollment of the remaining subjects. All enrolled subjects (run-in subjects and trial subjects) will be included in the final analysis.		
DURATION OF PARTICIPATION/STUDY	Each patient's individual participation will last approximately 20-48 hours.  It is expected the entire study will take approximately two (2) months to complete.		
STUDY ENDPOINTS	Primary Endpoint:		
	Procedure success: Nasoenteral tube (NET) can be placed in the correct anatomical position without occurrence of guidance-related adverse events.		

Version 1.3 NUTRI-002 July 11, 2018

	Additional Assessments:				
	Procedure Metric s: Number of placement attempts required				
	Safety: Adverse Events				
Sample Size Considerations	There is no statistically based sample size for this study which is being conducted to obtain confirmatory evidence to support the safety of using the ENVUE System as an adjunct to current placement practices for nasoenteral feeding tubes. Forty (40) to Fifty (50) subjects (includes run-in subjects) completing the Procedure Visit (NasoEnteral Tube placement procedure) will provide evidence that the NET tube guidance system does not present new or different safety issues as compared to the predicate (confirmatory study). If less than 35 patients will complete the Follow-up Visit (confirmation of tube tip anatomical location), an enrollment of another 5 patients will be considered.				
SCHEDULED VISITS	This study is an acute safety assessment of the ENVUE System covering the guidance functionality of the System.  Screening The screening visit will occur at time zero and will assess eligibility for the study and				
	obtain informed consent.  Procedure  The study procedure may occur within two days of screening. Informed consent will be affirmed and the patient will be considered enrolled.				
	Final Follow Up The final follow-up visit will occur 20-48 hours following the procedure.				
Inclusion Criteria	
 
Patients must be ≥21 years of age
 
Patients must require placement of a nasoenteral feeding tube
 
Patients have an endotracheal tube, OR         
 
Do not have an endotracheal tube but are sedated and/or classified as obtunded¹ at the time of placement
 
 
 
Patients or legal authorized representative must be able to understand and
 
				
	adhere to all protocol procedures and be willing and able to provide written informed consent 				

Obtundation level evaluation is based on Glasgow-Coma scale with a score of between 9 and 12. Sedation level is based on Richmond Agitation-Sedation Scale (RASS) score of -2 or less.
Consent may be provided by patient's legal authorized representative.

 NUTRI-002
 Version 1.3

 July 11, 2018

	Patients must not have a history of:				
EXCLUSION CRITERIA	
 
Esophageal varices or ulcers
 
				
	
 
Upper airway obstruction
 
				
	
 
Upper GI stenosis or obstruction
 
				
	
 
Trauma involving sinuses, nares face or neck that would prevent NG
 
				
	or oral tube insertion				
	
 
Deformities of the sinus cavities and/or skull base
 
				
	
 
Esophageal cancer or neoplasm
 
				
	Patients must not have a significant concomitant illness that would adversely				
	affect their participation in the study				
	Female patients who are pregnant or lactating				
STATISTICAL ANALYSIS	All data will be reported using summary statistics.				
OTHER CONSIDERATIONS	No core lab will be charted for this study; thus, judgements regarding placement will be based on the investigator's assessment of X-Ray images. Assessments of relatedness of any noted adverse events to the study device will be adjudicated by a Clinical Events Committee (CEC). No DSMB will be chartered for this study based on the well-understood safety profile.				
US REGULATORY STATUS	The ENVUE System is considered a non-significant risk investigational device in the United States.				

Version 1.3 NUTRI-002 July 11, 2018

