# 2 STATISTICAL CONSIDERATIONS

# 2.1 STATISTICAL HYPOTHESES

There is no formal statistical hypothesis for the primary endpoint of this feasibility trial. The primary endpoint is defined as procedure success, e.g., NET tube can be placed in the correct anatomical position without occurrence of guidance-related adverse events.

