### 2.2 SAMPLE SIZE DETERMINATION

This feasibility trial will include forty (40) to fifty (50) patients completing the Procedure Visit (NasoEnteral Tube placement) and at least five operators. ENvizion nasoenteral feeding tubes will be placed in 5 run-in subjects prior to enrollment of the remaining subjects. All enrolled subjects (run-in subjects and trial subjects) will be included in the final analysis. Patients or patients' LAR who chose not to participate after informed consent but prior to procedure, and patients who because of system malfunction or because of undiscovered or unreported physical reasons (e.g. deteriorating health, anatomical anomalies, mechanical obstruction, etc.) cannot complete the Procedure Visit (NasoEnteral Tube placement) will be considered Screen Failures, not be considered in the total patient count, but will be reported in the ITT dataset as defined below. If less than 35 patients will complete the Follow-up Visit (confirmation of tube tip anatomical location), an enrollment of another 5 patients will be considered.

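### The synopsis promises confirmatory evidence against the predicate, but the design is a descriptive single-arm feasibility study with no benchmark

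*Combined protocol and SAP*

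**What the plan says.** The Sample Size Considerations entry in section 1.1 makes two statements side by side. The first is a disclaimer that also states a purpose: "There is no statistically based sample size for this study which is being conducted to obtain confirmatory evidence". The second says what the 40 to 50 subjects completing the Procedure Visit will show: they "will provide evidence that the NET tube guidance system does not present new or different safety issues as compared to the predicate (confirmatory study".

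Elsewhere the plan describes a different kind of study:

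- The title in section 1.1 reads "A Feasibilty Study to Evaluate the Clinical Safety".
- The Study Design entry says "The study is a prospective, single center, non-randomized clinical trial".
- Section 2.1 says "There is no formal statistical hypothesis for the primary endpoint of this feasibility trial".
- Section 2.2 uses the same label: "This feasibility trial will include forty (40) to fifty (50) patients completing the Procedure Visit".
- The Statistical Analysis entry of the synopsis says "All data will be reported using summary statistics". Section 2.4 names the summaries (means, standard deviations, medians, ranges, counts, percentages) and says procedure success will be calculated in every population. It names no confidence interval.
- Under Other Considerations, "Assessments of relatedness of any noted adverse events to the study device will be adjudicated by a Clinical Events Committee".

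**The concern.** The second sample-size sentence states a conclusion about the predicate, and states it before any data exist. Such a conclusion needs something to compare with: a control arm, a predicate event rate, a margin or performance goal, or at least a written rule for deciding when a safety issue counts as new or different. None of these appears.

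What is at stake is how the result will be read. Safety is the study's stated objective, and this sentence is the only justification given for the number of subjects. If no guidance-related events occur, the plan's own wording invites the reader to take this as confirmation that the device is no different from the predicate on safety. A sample of 40 to 50 can reveal common guidance problems but cannot rule out uncommon ones, and the plan does not commit to reporting anything that would show this limit.

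**Working it through.** **Is there a figure to reproduce?** No. The plan gives no significance level, power, event rate, effect or margin, and says the sample size has no statistical basis. The check therefore has two parts: whether the plan contains what the claim needs, and what 40 to 50 subjects can show.

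**Part 1: what the claim needs and what the plan contains**

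| Needed for a confirmatory comparison | In the plan |
|---|---|
| Hypothesis or decision rule | Section 2.1: none |
| Comparator arm | Section 1.1: non-randomized; no control arm described |
| Predicate rate, margin or performance goal | None found |
| Rule for judging an issue new or different | None found |
| Measure of uncertainty | Sections 1.1 and 2.4: summary statistics, no interval |

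**Part 2: what 40 to 50 subjects can show**

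Inputs: n = 40 and n = 50 come from sections 1.1 and 2.2. The two-sided 95% level is my assumption. Subjects are treated as independent.

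*Zero events.* The exact (Clopper-Pearson) two-sided 95% upper limit is 1 − 0.025^(1/n).

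- n = 40: 1 − 0.025^(1/40) = 8.81%
- n = 50: 1 − 0.025^(1/50) = 7.11%

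As a check, the probability of zero events when the true rate equals the limit is 0.025 in both cases. With a one-sided 95% limit, 1 − 0.05^(1/n), the results are 7.22% and 5.82%. The Wilson two-sided limits are 8.76% and 7.13%, so the choice of method hardly matters. At n = 35, the follow-up completion threshold in sections 1.1 and 2.2, the exact two-sided limit is 10.0%.

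*One event.* The two-sided upper limit solves (1 − p)^n + n·p·(1 − p)^(n−1) = 0.025. It is 13.16% at n = 40 and 10.65% at n = 50.

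*All procedures successful.* The two-sided lower limit is 0.025^(1/n): 91.19% at n = 40 and 92.89% at n = 50.

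*Chance of seeing no event, (1 − p)^n.* The true rates p are assumed, since the plan gives none.

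| Assumed true rate | n = 40 | n = 50 |
|---|---|---|
| 1% | 66.9% | 60.5% |
| 2% | 44.6% | 36.4% |
| 5% | 12.9% | 7.7% |

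*Rate at which seeing and missing the event are equally likely.* Solving (1 − p)^n = 0.5 gives p = 1 − 0.5^(1/n): 1.72% at n = 40 and 1.38% at n = 50. Event types rarer than this would more likely than not go unseen.

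**The case against.** The best defence is that the claim is qualitative. *New or different* most naturally refers to kinds of safety issue, not to rates, and the sentence speaks of providing evidence, not of demonstrating equivalence or non-inferiority. On that reading, adverse event collection at both post-screening visits and adjudication by the Clinical Events Committee are relevant. The disclaimer about sample size also stands one sentence before the claim, so a careful reader is warned.

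Part of this stands. The plan does not use the language of equivalence, the disclosure is real, and neither a hypothesis nor a powered sample should be asked of a feasibility study. Leaving out an interval, taken alone, would only merit a suggestion.

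The qualitative reading still does not rescue the sentence. The text gives no list of the predicate's known issues and no method for judging novelty. The committee's described task is the relatedness of events to the study device, not comparison with the predicate. A qualitative review also cannot assess a kind of event that does not occur in the sample. Nor does the disclaimer supply the comparison that the next sentence claims.

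It is also fair to say that a predicate rationale may exist elsewhere: the opening pages were not available to this review, and the text seen has no background or risk-analysis section. The statement that no predicate rate is given is limited to that text. The conflict between the confirmatory wording and the descriptive design does not depend on it.

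**Conclusion.** The concern holds. The synopsis attributes to the study a confirmatory, comparative property that its design and analysis do not have. This is an error in the stated claim, not a missing detail, and it should be corrected. It does not prevent the study from being run as designed.

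The gap between claim and precision is material. A clean result in 40 to 50 subjects leaves guidance-related event rates of roughly 7% to 9% unexcluded. A single event raises that to roughly 11% to 13%.

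These figures assume a two-sided 95% level and independent subjects. A one-sided convention lowers the zero-event limits to between about 6% and 7% and changes nothing in the conclusion. At least five operators will place tubes, so any positive correlation within operator would make the real precision worse than shown.

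**What to change.** In section 1.1, Sample Size Considerations, remove the word *confirmatory* from both sentences and remove the claim against the predicate. Replacement text could read:

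> Forty to fifty subjects completing the Procedure Visit will provide descriptive safety data; no formal comparison with the predicate is made. If no guidance-related adverse events are seen, the exact two-sided 95% upper limit on the event rate, treating subjects as independent, is 8.8% (n = 40) or 7.1% (n = 50).

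In section 2.4, add exact (Clopper-Pearson) two-sided 95% intervals for procedure success and for the proportion of subjects with any guidance-related adverse event. Show the actual denominator for each population reported, because the sets defined in section 2.3 may differ in size from 40 or 50.

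The cost is a weaker stated claim and two intervals per population, so at most 2 × 3 = 6 across the three populations in section 2.3. No additional patients, procedures or data are needed.

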# Procedure (within 2-days of screening)

- Collect pre-procedure vital signs
- •Place NasoEnteral Tube using ENVUE System
- Collect procedure information (including number of tube replacement events)
- •Confirm placement via X-Ray (within 5 hours)
- Assess for adverse events and device related side effects

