# Follow-up (20-48 hours post procedure)

- Collect vital signs
- Confirm tube location using ENVUE System and X-Ray
- •Collect information regarding tube migration and reposition
- •Assess for adverse events or device related side effects

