**Table 1: Study Schedule** 

Procedures, Evaluations and	Study Visits			
Tests	Screening	Procedure (Within 2 days of Screening Visit)	Follow-up (20-48 hours after Procedure Visit)	
Informed Consent	X	X 		
Inclusion/Exclusion Criteria	Χ			
Demographics	Χ			
Medical History (Acute and Past)	X			
Concomitant Medications 	Х			
Examinations				
Targeted Physical Exam	Χ			
Vital Signs		X	X	
ENvizion™ nasoenteral tube		Х		
Placement		Λ		
Confirm Anatomical Location				
ENVUE System			X	
Abdominal and/ or thoracic X-		X 6	X	
ray 		^	^	
Adverse Events		X	X	

<sup>3 Affirmation of informed consent is only required if procedure visit is independent of screening visit.

<sup>4 Limited to sedatives/any medication with sedative effect, anticoagulants and prokinetic agents.  Additional X-Rays may be taken if clinically indicated.  Within five hours of placement.

Version 1.3 NUTRI-002 July 11, 2018

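### Adverse-event collection ends at a visit anywhere from 20 to 48 h after placement, so observation time can differ 2.4-fold while events are reported as plain counts and percentages

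*Combined protocol and SAP*

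**What the plan says.** The study's objective is safety, and the synopsis lists adverse events as the safety assessment. Under Scheduled Visits, "The final follow-up visit will occur 20-48 hours following the procedure". The column heading in Table 1 agrees ("Follow-up (20-48 hours after Procedure Visit"), and so does the stated duration: "Each patient's individual participation will last approximately 20-48 hours".

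The schema in section 1.2 has two adverse-event checks. At the procedure: "Assess for adverse events and device related side effects". At follow-up: "Assess for adverse events or device related side effects". The next box is Study Exit. Table 1 ticks adverse events in those two columns and has no later column.

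The primary endpoint is that the tube "can be placed in the correct anatomical position without occurrence of guidance-related adverse events", with no time window given for the adverse-event part. Section 2.4 plans counts and percentages for categorical variables and does not mention time observed. The synopsis (Other Considerations) gives the CEC the task of judging whether noted adverse events are related to the device.

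**The concern.** A 28 h window is reasonable for a tube-location check. The same window also sets when safety observation stops. A subject seen at 20 h and one seen at 48 h count equally in the adverse-event denominator, although the first was watched for less than half as long. An event at 30 h would be counted in the second subject and not in the first.

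The adverse-event proportion therefore depends partly on when visits happen to be held, and the report would not show this because observation time is not summarised. The sample-size paragraph says that 40 to 50 subjects will provide evidence of no new or different safety issues compared with the predicate. With so few subjects, one or two events matter to that reading.

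A smaller gap concerns events first noted at the last visit. They are recorded, but no later data collection is scheduled to tell the CEC how they evolved.

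**Working it through.** The plan has no figure to reproduce: the sample size is stated to have no statistical basis, and no event rate is given.

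**Inputs from the documents.** Follow-up at 20-48 h (Scheduled Visits, schema, Table 1); 40 to 50 subjects completing the Procedure Visit (synopsis, section 2.2); counts and percentages (section 2.4).

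**Assumed inputs.** The 48 h risk of a post-insertion event, p48, is varied from 2% to 20%. The hazard is either constant or front-loaded (Weibull with shape k = 0.5 or 0.25). Events apparent at insertion are outside this calculation, since every timing captures them.

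**Step 1, spread of observation time.** 48/20 = 2.4-fold; 48 − 20 = 28 h. Total observation for 40 subjects lies between 40 × 20 = 800 and 40 × 48 = 1920 patient-hours; for 50 subjects, between 1000 and 2400.

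**Step 2, share of the 48 h risk seen by 20 h.** The formula is p20 = 1 − (1 − p48)^((20/48)^k), where k = 1 is the constant hazard. The exponents are 20/48 = 0.417 (k = 1), 0.645 (k = 0.5) and 0.803 (k = 0.25).

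| p48 | p20, constant (share) | p20, k = 0.5 (share) | p20, k = 0.25 (share) |
|---|---|---|---|
| 2% | 0.84% (42%) | 1.30% (65%) | 1.61% (80%) |
| 5% | 2.11% (42%) | 3.26% (65%) | 4.04% (81%) |
| 10% | 4.30% (43%) | 6.57% (66%) | 8.12% (81%) |
| 20% | 8.88% (44%) | 13.41% (67%) | 16.41% (82%) |

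A 20 h visit thus captures about 42-44% under a constant hazard and about 65-82% under the front-loaded ones.

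**Step 3, a mixed schedule.** If visits are spread evenly over 20-48 h (mean 34 h) and the hazard is constant, average capture at p48 = 5% is 3.56%/5% = 71%.

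**Step 4, what this does in 40 subjects.** Take p48 = 5%. Observing everyone to 48 h gives 40 × 0.05 = 2.0 expected events and a chance of at least one of 1 − 0.95^40 = 87%. If everyone is seen at 20 h:

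- constant hazard: 40 × 0.0211 = 0.85 expected events; chance of at least one 1 − 0.95^(40 × 0.417) = 57%
- k = 0.5: 1 − 0.95^(40 × 0.645) = 73%
- k = 0.25: 1 − 0.95^(40 × 0.803) = 81%

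The all-at-20-h case is the extreme of the permitted window, not a forecast.

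**The case against.** The strongest defence is the study's own scope: "This study is an acute safety assessment of the ENVUE System covering the guidance functionality of the System". The endpoint concerns placement and guidance-related events, placement is confirmed by X-ray within five hours, and everyone who completes follow-up has at least 20 h. The study is descriptive, with no control arm and no hypothesis, so unequal follow-up cannot bias a comparison within it. Much of this stands, and it is why the primary endpoint is probably little affected. It justifies a short window, though, not one whose length varies by subject.

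It is also fair that a constant hazard suits placement-related events poorly. The front-loaded columns are the more plausible ones for such events, and their loss is smaller.

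The text available is a summary plus the statistical section. If a fuller adverse-event section exists with a fixed cut-off and a rule for following events, only alignment of Scheduled Visits and Table 1 is needed.

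A reader might infer several stronger points that the documents do not support:

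- **That sites scheduling early would report fewer events.** The study has a single center.
- **That findings on the last X-ray, or events still open, are lost.** The film and the adverse-event check belong to the same visit, before exit. Both can be recorded; only the later course is unseen.
- **That tubes are repositioned at the final visit and then left unobserved.** The schema says "Collect information regarding tube migration and reposition", which describes data collection and fits repositioning at any time since placement.
- **That participation is misstated and should include the days from screening.** The synopsis treats a patient as enrolled at the procedure, so 20-48 h is consistent with it.

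**Conclusion.** The point holds as a gap in safety data collection. Adverse-event observation varies up to 2.4-fold between subjects, no fixed cut-off is written, and the planned summaries do not show the variation. Events arising after an early visit but within 48 h go uncaptured, and the course of an event first noted at the last visit is not scheduled to reach the CEC.

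The 2.4-fold figure follows directly from the visit window. The capture shares at 20 h depend on assumed hazard shapes and risks, because the documents supply neither. The effect falls mainly on the adverse-event summary. The primary endpoint should change little if guidance-related events cluster near insertion, but no endpoint window is written to confirm that. The change is worth making because safety is the study's objective and the remedy is cheap.

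**What to change.** In Scheduled Visits and Table 1, separate the two purposes of the last visit:

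1. Keep the tube-location check at 20-48 h.
2. Collect adverse events for every subject by chart review to a fixed 48 h after placement, or to discharge or death if earlier.
3. Record each subject's observation time, and add to section 2.4 that it is reported beside the adverse-event proportion.
4. For any event open at 48 h, or first noted at the follow-up visit, record its outcome from the chart for the CEC.

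This alters data collection only. It makes the observation period equal rather than longer: a subject seen at 48 h gains nothing beyond item 4. The cost is protocol and case-report-form wording and one brief chart look per subject seen before 48 h. The event count may come out slightly higher.

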### 1.2 SCHEMA

# Figure 1: Study Flow Chart

# Screening

- Obtain informed consent
- •Assess inclusion/exclusion criteria
- Capture baseline demographics, medical history and concomitant medications
- Collect clinical assessments (height, weight, previous X-Ray interpetation if available)

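### Does it matter that sedation or obtundation must hold at placement, while the schedule marks the eligibility check at Screening only?

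*Combined protocol and SAP*

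**What the plan says.** The Inclusion Criteria in section 1.1 (Synopsis) give two routes into the study. A patient either has an endotracheal tube, or has none and meets a second condition: "but are sedated and/or classified as obtunded¹ at the time of placement". The footnote sets the scales. Obtundation means a GCS score of 9 to 12, and for sedation: "Sedation level is based on Richmond Agitation-Sedation Scale (RASS) score of -2 or less".

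On timing, Scheduled Visits in section 1.1 puts the eligibility assessment at Screening and adds: "The study procedure may occur within two days of screening". Of the Procedure Visit it says: "Informed consent will be affirmed and the patient will be considered enrolled".

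The schema (section 1.2, Figure 1) has "Assess inclusion/exclusion criteria" in the Screening box and does not repeat it under Enrollment or Procedure. The Screening box also has "Collect clinical assessments (height, weight, previous X-Ray interpetation if available"; the Procedure box opens with "Collect pre-procedure vital signs". In Table 1 the row "Inclusion/Exclusion Criteria" is marked under Screening alone. The consent row is marked twice, and footnote 3 limits the second mark to the case where the two visits are separate.

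**The concern.** Most of the entry criteria concern history or stable traits, and a check two days old is as good as a fresh one. Level of consciousness is different, because it can change within hours. The sponsor tied this criterion to the moment of placement, yet every part of the plan that schedules an eligibility check puts it at Screening. Where the visits are separate, the plan calls for consent to be affirmed again but says nothing about this criterion. RASS and GCS appear only in the footnote that defines them.

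A patient without a tube might therefore meet the criterion at Screening, no longer meet it a day or two later, and still have a tube placed. If nobody noted the deviation, section 2.3 would leave that patient in the Per-Protocol set as well as the ITT set, because the Per-Protocol set drops only patients with noted deviations. The report could not then show that everyone studied belonged to the population the criteria describe. Consciousness at placement is also hard to reconstruct afterwards.

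**Working it through.** The plan gives no figure to reproduce on this point, so the check sets the passages side by side and then bounds the effect.

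**Schedule (Table 1, three visits).**

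| Item | Visits marked |
|---|---|
| Eligibility criteria | 1 of 3 (Screening) |
| Informed consent | 2 of 3 (Screening; Procedure if separate) |
| Targeted physical exam | 1 of 3 (Screening) |
| Concomitant medications, including sedatives (footnote 4) | 1 of 3 (Screening) |
| RASS or GCS as a row of its own | 0 of 3 |

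The last line needs care. Table 1 uses one row for all entry criteria and gives none of them its own row; pregnancy and oesophageal varices have none either. The zero shows how coarse the table is. It does not show that no score is taken.

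**Gap between check and placement.** It is 0 hours if the visits are combined and up to 2 × 24 = 48 hours if they are separate. Section 1.1 puts each patient's participation at about 20 to 48 hours, which equals the follow-up window after the procedure. If participation is counted from Screening, that leaves roughly 0 hours for the gap (20 − 20 and 48 − 48). If it is counted from the procedure, the figure says nothing about the gap. The documents do not say which, so this suggests a short gap without proving it.

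**Who could be affected.** Taking the cases in turn:

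1. Tube in place at placement: the RASS/GCS condition does not apply.
2. No tube, visits combined: the Screening check is close to placement.
3. No tube, visits separate, still sedated or obtunded: the criterion is met.
4. No tube, visits separate, condition lapsed, criterion applied as written: no placement.
5. As case 4, but placed and noted: a protocol deviation, so out of the Per-Protocol set and kept in ITT.
6. As case 5, but not noted: the patient stays in both sets.

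A patient extubated between the visits simply moves to the no-tube route and falls under cases 3 to 6. Only case 6 does harm. It requires five things together: no tube, separate visits, a lapse, placement despite the criterion, and no note of it. The documents give no frequency for any of them.

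**Size of one case-6 patient.** Let *s* be the successes among *n* patients.

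- Removing one failure changes the proportion by *s*/(*n* − 1) − *s*/*n* = *s*/[*n*(*n* − 1)], which is largest at *s* = *n* − 1 and then equals 1/*n*.
- Removing one success changes it by (*n* − *s*)/[*n*(*n* − 1)], which is also at most 1/*n*.
- With *n* = 50, 1/50 = 2.0 percentage points. With *n* = 40, 1/40 = 2.5 points. For example, 39/40 = 97.5% becomes 39/39 = 100%.

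These are ceilings per patient. A Per-Protocol set smaller than 40 would have a somewhat higher one. They hold for any single misclassified patient and are not evidence that one exists.

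**The case for a change.** The best argument for acting is that knowing a rule and recording that it was met are different things. Staff may apply the criterion faithfully, yet the schedule asks for no entry that would show it. The sponsor did foresee separate visits, since consent is to be affirmed again, and left out the one criterion expressly tied to placement. Section 2.4 calculates procedure success for every population, so Per-Protocol membership feeds a reported result. A single footnote would cost almost nothing.

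The textual mismatch stands, and such a footnote would be harmless housekeeping. The need for it does not follow. The criterion carries its own time point and enrolment falls at the Procedure Visit, so no rule lapses between the visits. An unrecorded deviation escapes any per-protocol set, however the schedule is drawn. The item for collecting procedure information in the schema is open-ended, although it names only tube replacement events, and the case report forms and detailed procedures are not in the text available here. Absence from a summary table therefore cannot establish that nothing is recorded.

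Going further and writing new analysis-set rules could do harm. To declare that a patient who fails a check before placement is not enrolled would conflict with section 1.1, where affirming consent at the Procedure Visit already makes the patient enrolled. How screen failures in section 2.2 fit the ITT definition in section 2.3 is a separate question and does not depend on this point.

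**Conclusion.** No change to the plan is called for. The schedule is less specific than the criterion, but the criterion governs: read as written, it must be met at placement, and no stated number or rule gives a wrong result. The exposure is limited to patients without an endotracheal tube whose visits are separate, with a gap of at most two days. Their number cannot be derived from the documents and may be zero. Each undetected case could shift a reported success percentage by no more than 2.0 to 2.5 points with 50 to 40 patients. Section 2.1 sets no hypothesis and section 1.1 no statistically based sample size, so no test or error rate is affected; the only effect is on how the descriptive result is read.

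This rests on two assumptions: investigators apply the criterion at the time it names, and a placement known to breach it is noted as a deviation. Both are ordinary conduct under the plan as it stands. No view is taken on the clinical thresholds.

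### The X-ray read behind the placement component of the primary endpoint is not required to be separate from the placing operator or masked to the ENVUE display

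*Combined protocol and SAP*

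**What the plan says.** The synopsis (section 1.1, Study Endpoints) defines procedure success as: "Nasoenteral tube (NET) can be placed in the correct anatomical position without occurrence of guidance-related adverse events". Section 2.1 repeats this definition. It has two components, tube position and freedom from guidance-related events.

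The Other Considerations row of the synopsis says that there is no core lab and that "judgements regarding placement will be based on the investigator's assessment of X-Ray images". The same row sends the relatedness of adverse events to a CEC. Position is not sent there.

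The tubes are placed "at a single center by at least five operators", and section 2.2 also gives the minimum of five. On design, the synopsis says: "The study is a prospective, single center, non-randomized clinical trial in patients that require placement of a nasoenteral feeding tube".

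The flow chart in section 1.2 and Table 1 call for an X-ray within five hours of placement. At the 20-48 hour follow-up they call for a second X-ray and a location check with ENVUE. Neither names the reader, sets an order for the two follow-up checks, or mentions masking.

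**The concern.** Position is judged by a person from an image. If that person placed the tube, or has seen where ENVUE showed the tip, they come to the film with an expectation. A doubtful film may then be called correct more readily than it would be by someone who had only the film. The system under test would also be informing the reference standard used to score it.

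With no comparator arm, there is no second group in which the same lean would occur and cancel. It would go directly into the single reported proportion. That matters because the sample-size row of the synopsis presents the data as confirmatory support for safety relative to the predicate, so others are expected to rely on the success rate.

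**Working it through.** **Is reader separation stated anywhere?** I looked through the supplied text for any rule on who reads the film.

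| Question | What the documents give |
|---|---|
| Who judges position? | The investigator, from X-ray (synopsis, Other Considerations) |
| Who places tubes? | At least five operators at one center (synopsis; section 2.2) |
| Must the reader differ from the placing operator? | Not stated |
| Is the reader masked to the ENVUE display or procedure record? | Not stated |
| Is there a second read, or comparison with a radiology report? | None planned |
| What does the CEC review? | Relatedness of adverse events, not position |

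The gap is therefore one of silence. Overlap between operator and reader is neither described nor excluded.

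**How much can one film matter?** The plan has no figure to reproduce: no hypothesis (section 2.1), no performance goal, and a sample size stated not to be statistically based. The only input is n = 40 to 50 patients completing the Procedure Visit (section 2.2).

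If k films are called correct that should not have been, and those patients had no guidance-related event, the success rate rises by 100 × k / n percentage points.

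- n = 40, k = 1: 100 × 1/40 = 2.5 points
- n = 50, k = 1: 100 × 1/50 = 2.0 points

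These are the most that one film can add at these sizes. If the patient also had a guidance-related event, the composite is already a failure and the read changes nothing.

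**Effect on precision, for scale only.** The failure counts and the 95% level below are my assumptions; the plan specifies no interval. The limits are exact (Clopper-Pearson, two-sided).

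| n | Successes | Rate | Lower 95% limit |
|---|---|---|---|
| 40 | 38 | 38/40 = 95.0% | 83.1% |
| 40 | 40 | 40/40 = 100% | 91.2% |
| 50 | 48 | 48/50 = 96.0% | 86.3% |
| 50 | 50 | 50/50 = 100% | 92.9% |

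Two favourable calls would raise the lower limit by 91.2 − 83.1 = 8.1 points at n = 40 and by 92.9 − 86.3 = 6.6 points at n = 50. This shows sensitivity; it does not predict how many films would be misread.

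**The case against.** A reader might infer that operators grade their own placements. The documents do not support that. They use different terms for the people who place tubes (operators) and the person who judges films (the investigator), and never say that one is the other. If the reading investigator places no tubes, the separation from the operator already exists in practice. This part of the objection stands: what can be said is that separation and masking are not required.

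A reader might also infer that the X-ray read decides the whole endpoint. It decides position only. The adverse-event component depends on relatedness, which goes to the CEC.

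Nor does having at least five operators show that a qualified non-placing reader is always on hand, since nothing says operators are investigators or can read films. The remedy has to allow for that.

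The study is descriptive, with no hypothesis and no pass/fail threshold, so a few favourable reads would not turn a failed trial into a successful one. An X-ray is a fairly objective, retained record, and doing without a core lab is an openly stated choice. The 20-48 hour film adds a second image, though not a second reader, and the tube may have moved by then. These points reduce the weight of the concern. They do not remove it, because the rate will still be reported and used as supporting evidence.

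Finally, the supplied text gives no written criteria for correct position. A separate reader would still be exercising judgement, so the change below reduces expectation bias without removing all subjectivity.

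**Conclusion.** The concern holds in a limited form. The placement component of the primary endpoint rests on an investigator's X-ray read that the documents neither separate from the placing operator nor mask to ENVUE output. In a study with no comparator arm, an unmasked read could inflate the success rate by up to 2.5 points per re-called film at n = 40 and 2.0 at n = 50. The total inflation cannot be estimated, because the number of such films is unknown.

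This rests on two assumptions: that the film taken within five hours of placement is the one that scores the endpoint, and that some films leave room for judgement. The finding is an unprotected read, not evidence that biased reading will occur. It is worth correcting because the correction is cheap; it does not invalidate the design.

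**What to change.** In the Other Considerations row of the synopsis, state that:

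1. the endpoint read is made from the X-ray without the ENVUE display or the procedure record; and
2. it is made by an existing site investigator who did not place that patient's tube, wherever one is available.

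On the CRF, record whether the reader placed the tube. Where a radiology report of the same film already exists, transcribe its tip location and list any disagreement with the investigator's read in the final report.

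This needs no core lab, added reader, extra X-ray or change in sample size. The cost is one or two CRF fields and the scheduling of an endpoint read after the clinical read, so clinical use of the film is not delayed. If separate reading is already the site's practice, the change simply documents it.
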